Aim 3: Recruitment will take place over 15 months. We anticipate enrolling groups of 5 - 10 subjects based on preferences defined in Aim 1. During visit one, we will collect baseline demographic data, baseline questionnaires, and have viral load assessments on all participants. The second research visit will take place 6 months after randomization. This research visit will evaluate acceptability and feasibility and perform in-depth interviews exploring the UTAUT model of technology acceptance with all participants in the experimental arm.(37) In addition, all subjects will complete follow-up questionnaires and have viral load assessment.

Data to be collected and when the data is to be collected

Demographic data will be collected on all adolescents during a chart review and will include age, sex, age at diagnosis, history of opportunistic infections, length of time on ART, ART regimen, last viral load, last clinic visit, and last pharmacy refill. Data will be collected from a combination of electronic records (Tier.net and NHLS) and paper charts. Additional data on vital status and location of care services will be obtained through the tracker program. Only de-identified data will be entered into the database. Viral load will be measured at enrollment and 6 months after randomization. Pharmacy refill and clinic appointment data will be collected during enrollment in the study.

InTSHA: Interactive Transition Support for HIV-infected Adolescents Using Social Media - Detailed Protocol

Aim 4: We will recruit participants from adolescents who participated in AIM 1 interviews, and from Mahatma Gandhi Hospital's and KwaMashu Poly Clinic's Pediatric and Adult HIV Clinics.

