Aim 3: We will determine the primary outcomes of acceptability (quantitative assessment of acceptability based on the UTAUT developed by [name])(29, 31) and feasibility (enrollment, participation and completion thresholds >80% for each). We will also measure secondary outcomes of retention in care (pharmacy refill and clinic attendance in last 6 months) and viral suppression (<400 copies/ml) comparing pre-transition with 6 months after randomization. In addition, we will explore other factors based on modifiable variables in the SMART model including: adolescent peer support (Child and Adolescent Social Support Scale),(39) self-esteem (Rosenberg scale),(40) depression (PHQ-9),(41) and stigma (Internalized AIDS stigma scale),(42) connection to clinic (Working Alliance Inventory),(43) and transition readiness (TRANSITION Q).(44)

Aim 4: In-depth interviews will examine the different mechanisms of stigma and its impact on engagement in HIV care, including retention in care, adherence to medications, and viral suppression. We will aim for thematic saturation in each group.

Aim 5: I will use an iterative process as described in Aim 2 after each focus group session with adolescents to evaluate feedback for each version of the stigma-based intervention based on coded themes identified during focus group feedback sessions. The stigma content will be revised based on focus group feedback prior to demonstration with the second focus group. The final stigma intervention content will be based on the iterative process from both focus groups, as well as input from our collaborative research team.

Aim 6: A targeted questionnaire assesses sexual and reproductive health behaviors and attitudes, adapted from the WHO Framework for asking about SRH with Adolescents.

Aim 7: In-depth interviews will examine the adolescent attitudes about sexual and reproductive health and its impact on engagement in HIV care, including sources of information about sex, access to sexual health resources, personal experiences with relationships, and communication about reproductive health. We will aim for thematic saturation in each group.

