Aim 3: Our primary focus is on estimating the acceptability and feasibility of the social media intervention for planning a larger clinical trial to measure efficacy. We will consider a feasibility / acceptability estimate of 80% or higher among the 40 participants as evidence that the social media program is acceptable to the population. Analysis. We will summarize the acceptability and feasibility data in the intervention group using standard summary statistics (e.g. counts/percentages; median and interquartile range of continuous measures). We will estimate the difference between the intervention group and the control for social support, connection to clinic, self-esteem, retention in care and virological suppression 6 months after randomization. The secondary outcomes will assist in planning a larger randomized clinical trial through a future R01 grant; the standard deviation for these differences is expected to be on the order of 8%. Depending on the number of individuals not retained in care or the number not virologically suppressed, we may use logistic regression to explore combinations of 2-3 variables potentially predictive of outcome. Assuming that the intervention is acceptable and feasible for participants, we would consider moving forward to an R01 if there was evidence of a benefit to participants, in terms of overall retention and virological suppression at 6 months, although we would not expect the difference to be statistically significant.

Power analysis (sample size, evaluable subjects, etc): With 40 participants in the experimental arm, if the true acceptability rate were 90% we would be able to rule out that acceptability was less than 70% with 90% power (alpha=0.05, one-sided) using an exact test.

Aim 4: We will use an inductive, content analytic approach to identify the different mechanisms of stigma and how they affect engagement in care during healthcare transition. Interviews will be recorded, transcribed, and translated into English. Transcriptions will be uploaded, organized, and coded using Dedoose software (version 7.0.23, LA, California).(52) We will use open coding to inductively construct descriptive categories based on themes identified in the interviews and then create a codebook based on themes identified in a subset of interviews. We will create categories based on the coded text using an iterative process and broader themes will be created using linking and framing of coded text.

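### The 80% acceptability benchmark (32 of 40) is looser than the exact test that justifies n = 40 (34 of 40), and no planned analysis shows whether 70% is ruled out

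*Combined protocol and SAP*

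**What the plan says.** All of this concerns Aim 3, the pilot randomised trial, in the combined protocol and SAP.

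- **Benchmark** (section VII, Statistical methods): "We will consider a feasibility / acceptability estimate of 80% or higher among the 40 participants as evidence" that the programme is acceptable to the population.
- **Sample size** (section VII, Power analysis), for 40 participants allocated to the intervention: "if the true acceptability rate were 90% we would be able to rule out that acceptability was less than 70% with 90% power", by an exact test at one-sided alpha 0.05. No critical count is given.
- **Planned analysis** (section VII, Statistical methods): "We will summarize the acceptability and feasibility data in the intervention group using standard summary statistics", with counts, percentages, medians and interquartile ranges as examples. Neither a test nor a confidence limit for acceptability is listed.
- **Measure** (section VII, Outcomes): acceptability is a "quantitative assessment of acceptability based on the UTAUT". No score is given above which a participant counts as accepting.
- **Feasibility** (section VII, Outcomes): "enrollment, participation and completion thresholds >80% for each". The benchmark in Statistical methods includes 80% itself.
- **Timing** (section VI, Study Procedures), on the visit 6 months after randomisation: "This research visit will evaluate acceptability and feasibility".

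**The concern.** The Aim 3 text holds two criteria for the same outcome and does not say how they relate. One is a point estimate of at least 80%. The other is exclusion of 70% by an exact test. Only the first is stated as a rule for a conclusion, so a reader will tend to attach the stated alpha and power to it. Those figures describe a stricter rule.

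Acceptability is a primary outcome, and an acceptable, feasible programme is one of the conditions for considering a larger trial. If 32 or 33 of 40 participants rate the programme acceptable, the plan lets the team report evidence of acceptability from a sample sized to exclude 70%, when the data do not exclude 70%. A report limited to summary statistics would not make that visible.

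**Working it through.** **Inputs.** From the Power analysis paragraph: n = 40, value to exclude p0 = 0.70, assumed truth p1 = 0.90, one-sided alpha 0.05, exact test. From Statistical methods: benchmark of at least 80%, so 0.80 × 40 = 32. Two assumptions are needed: each participant gives a yes/no acceptability result, and all 40 are evaluable.

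**Formulas.** With X ~ Binomial(n, p), a rule of at least c successes is met with probability P(X ≥ c | p) = Σ C(n,k) p^k (1−p)^(n−k), summed over k = c to n. At p0 this is the one-sided error; at p1 it is the power. The exact (Clopper-Pearson) one-sided 95% lower limit for x of n is the 5th percentile of Beta(x, n−x+1).

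**Step 1: reproduce the plan's figure.** The exact test uses the smallest c with P(X ≥ c | 0.70) ≤ 0.05.

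| Rule, n = 40 | Error at 70% | Power at 90% | Exact one-sided 95% lower limit at that count |
|---|---|---|---|
| ≥ 32 (80%) | 0.1110 | 0.9845 | 66.8% |
| ≥ 33 (82.5%) | 0.0553 | 0.9581 | 69.6% |
| ≥ 34 (85%) | 0.0238 | 0.9005 | 72.5% |

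A cut-off of 33 fails because 0.0553 > 0.05, so the critical count is 34. Its power is 0.9005, and the plan's 90% reproduces.

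**Step 2: the benchmark.** The rule of 32 or more has error 0.111, which is 0.111 / 0.05 = 2.2 times the stated alpha. Its power is 0.985, not 0.90.

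**Step 3: the counts where the two criteria disagree.** These are 32 and 33. Their probability is P(X ≥ 32) − P(X ≥ 34).

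| True acceptability | P(32 or 33 of 40) |
|---|---|
| 80% | 0.593 − 0.286 = 0.307 |
| 85% | 0.865 − 0.607 = 0.258 |
| 90% | 0.985 − 0.901 = 0.084 |

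**Step 4: fewer than 40 evaluable.** The plan gives no loss figure for this calculation, so the evaluable numbers below are assumed.

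| Evaluable | Exact cut-off | Error at 70% | Power at 90% | 80% rule | Error of 80% rule at 70% |
|---|---|---|---|---|---|
| 39 | 33 | 0.029 | 0.911 | 32 | 0.066 |
| 38 | 32 | 0.036 | 0.920 | 31 | 0.080 |
| 37 | 31 | 0.044 | 0.929 | 30 | 0.095 |
| 36 | 31 | 0.022 | 0.855 | 29 | 0.112 |
| 33 | 28 | 0.041 | 0.894 | 27 | 0.094 |
| 32 | 28 | 0.019 | 0.789 | 26 | 0.113 |

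Over every evaluable number from 30 to 40, the error of the 80% rule at a true 70% runs from 0.066 (n = 39) to 0.160 (n = 30). It is always above 0.05.

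**The case against.** The strongest reply is that nothing is miscalculated. The power figure is right, and the two statements can serve different purposes. The plan says its main interest is estimation, a pilot may use a point-estimate benchmark, and the power sentence stands under its own label with its own null value. The plan nowhere claims that 80% excludes 70%. An exact test with those inputs fixes its own cut-off, the list of summary statistics is given as examples only, and anyone with the count and the denominator can compute the limit. The practical effect is also modest: the larger trial further depends on evidence of benefit and is only something the team would consider, and at the assumed 90% truth the disputed counts arise about 8% of the time.

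Much of this stands. The 80% benchmark is legitimate, the power figure needs no correction, and 11.1% is the error of the acceptability statement, not of the decision to proceed. Losing one to three participants would not lower the exact test's power below 90%.

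It does not close the gap. The exact test appears only in the sample-size sentence, and the analysis text commits to neither the test nor a limit. A focus on estimation is itself a reason to report a confidence limit. If the test is intended, readers still need to be told that reaching 80% does not satisfy it.

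The missing yes/no definition is a fair complaint. The plan's own reference to an acceptability rate and an exact test implies a proportion, but how a participant is classed is not stated.

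**Conclusion.** The concern holds. The alpha and power used to justify n = 40 belong to a rule of 34 of 40, while the stated rule is 32 of 40. At a true 70% the stated rule is met 11.1% of the time, not 5% or less; at a true 90% it is met 98.5% of the time. Observed results of 80% and 82.5% meet the benchmark without excluding 70%, and no planned analysis would reveal it.

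The exact counts assume a yes/no rating and 40 evaluable participants. The mismatch remains at every evaluable number checked, from 30 to 40. This should be fixed, but it does not undermine the sample size. The difference between more than 80% and at least 80% is a separate, smaller inconsistency and applies to feasibility only.

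**What to change.** Keep the 80% benchmark if it is wanted, and add to the Aim 3 analysis text:

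1. Its properties: with a yes/no rating and all 40 evaluable, the benchmark has 11.1% one-sided error at a true 70% and 98.5% power at a true 90%, and does not by itself rule out 70%.
2. A reporting rule, for example: *The exact one-sided 95% lower confidence limit for acceptability will be reported. Acceptability below 70% will be described as ruled out only if this limit exceeds 70% (34 of 40 if all are evaluable; recomputed for the evaluable number otherwise).*
3. How a participant's UTAUT assessment is classed as acceptable or not, since the reporting rule cannot be applied without it.
4. One inequality for the feasibility thresholds, used in both Outcomes and Statistical methods.

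The cost is a few sentences, with no change to sample size, data collection or the benchmark. The downside is that an observed 80% to 82.5% would be reported as meeting the benchmark without excluding 70%, a less favourable statement. With all 40 evaluable that would happen 31%, 26% or 8% of the time at a true 80%, 85% or 90%.

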AIM 3: After the development of the behavioral intervention delivered through social media in Aim 2, we will offer enrollment to all adolescents living with HIV at Mahatma Gandhi Hospital and KwaMashu Poly Clinic after their physician determines that they are ready to transfer to adult care. Informed consent and assent will be obtained as in the above procedure. The consent/assent procedure will obtain consent for medical records review.

Adolescents will be randomized (1:1) to receive the behavioral intervention delivered via social media vs. standard of care. All participants will be shown how to password protect their mobile phones. Participants will complete a questionnaire at baseline and after six months to evaluate peer support, connection to clinic, depression, self-esteem and transition readiness. We will conduct in-depth interviews with adolescents in the intervention arm to assess acceptability. We will perform a medical records review and evaluate clinic attendance and viral load before and 6 months after the enrollment.

AIM 4: We will offer enrollment to adolescents living with HIV (ages 15-19 years old) accessing antiretroviral therapy at Mahatma Gandhi Hospital and KwaMashu Poly Clinic, those that have transitioned to adult care, and those who were lost to care as determined by a prior research study. Participants will be referred to study staff by HIV clinicians. We will also offer enrollment to adolescents who participated in in depth interviews for AIM 1 of this study. Participants will complete in-depth interviews exploring the different mechanisms of stigma using the HIV Stigma Framework, including enacted, anticipated, and internalized stigma, and its impact on their engagement in HIV care during healthcare transition.

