Aim 8: We will measure of retention in care (pharmacy refill and clinic attendance in last 6 months) and viral suppression (<200 copies/ml) comparing results from 6 months after randomization to 12 months after randomization. In addition, we will explore other factors based on modifiable variables in the SMART model including: adolescent peer support (Child and Adolescent Social Support Scale), (41) self-esteem (Rosenberg scale), (42) depression (PHQ-9), (43) and stigma (Internalized AIDS stigma scale), (44) connection to clinic (Working Alliance Inventory), (45) and transition readiness (HIV Adolescent Readiness for Transition). (46)

Aim 9: We will compare short term adherence (tenofovir levels) among adolescents in the InTSHA intervention group to the standard of care group. In addition, for viremic adolescents we will evaluate for the presence of HIV drug resistance searching specifically for Protease, Integrase, and Reverse Transcriptase mutations. We will use the Stanford database of HIV Drug resistance to determine significant HIV drug resistance mutations.

Modifiable factors from SMART model

- HIV knowledge
- Self-efficacy
- Beliefs
- Maturity
- Goals/Motivation
- Peer and social support
- Relationship with clinical staff
- Experience with HIV disclosure and stigma

Statistical methods

InTSHA: Interactive Transition Support for HIV-infected Adolescents Using Social Media - Detailed Protocol

Aim 1: We will use an inductive, content analytic approach to identify benefits and potential negative impacts of social media use during transition to adult care.(32, 51) Interviews will be translated from the local language (Zulu) into English and transcribed. Transcriptions will be uploaded, organized, and coded using Dedoose software (version 7.0.23, LA, California).(52) We will use open coding to inductively construct descriptive categories based on themes identified in the interviews. We will create a codebook based on themes identified in a subset of interviews. We will use an iterative process to construct categories based on the coded text. Broader themes will be created using linking and framing of coded text.

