Aim 8: We will summarize viral suppression and retention in care in the intervention and control groups using standard summary statistics (e.g. counts/percentages; median and interquartile range of continuous measures). We will estimate the difference between the intervention group and the control for social support, connection to clinic, self-esteem, retention in care and virological suppression 12 months after randomization. The standard deviation for these differences is expected to be on the order of 8%. Depending on the number of individuals not retained in care or the number not virologically suppressed, we may use logistic regression to explore combinations of 2-3 variables potentially predictive of outcome.

Aim 9: We will summarize adherence (tenofovir levels) and significant HIV drug resistance in the intervention and control groups using standard summary statistics (e.g. counts/percentages; median and interquartile range of continuous measures). Although this study is not powered to detect a significant difference in the intervention and control arms for adherence or drug resistance, this will provide valuable explanatory detail for the primary results of this study.

VIII. Risks and Discomforts

Risk: Loss of privacy is a potential risk if information is compromised which could lead to unintended disclosure of personal medical information including HIV status.

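### Aim 8 times its extra visit differently in the two arms, so its between-arm difference is not a clean 12-month contrast; enrollment values that could sharpen the Aim 3 and Aim 8 estimates have no committed use

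*Combined protocol and SAP*

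**What the plan says.** **Analysis.** Section VII, Statistical methods, Aim 3: "We will estimate the difference between the intervention group and the control for social support, connection to clinic, self-esteem, retention in care" and suppression, at 6 months. Aim 8 names the same outcomes, ending with "retention in care and virological suppression 12 months after randomization". Neither paragraph names an enrollment covariate, a change score or a committed model. Both allow an optional, exploratory logistic regression on two or three unnamed variables, depending on how many participants are not retained or not suppressed.

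**Data already collected.** Section IV, Aim 3: "Participants will complete a questionnaire at baseline and after six months to evaluate peer support, connection to clinic, depression, self-esteem and transition readiness". Section VI, Aim 3: "Viral load will be measured at enrollment and 6 months after randomization".

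**Outcome wording.** For retention and suppression, Section VII, Outcomes, Aim 3 has "comparing pre-transition with 6 months after randomization", with suppression below 400 copies/ml. Aim 8 has "comparing results from 6 months after randomization to 12 months after randomization", with suppression below 200 copies/ml. Neither sentence names the arms.

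**Timing of the Aim 8 visit.** Section IV, Aims 8/9, asks for one extra visit: in the intervention arm no sooner than a year after the intervention ends, in the control arm a year from randomization. Section II (Aim 8) and both Aim 8 paragraphs of Section VII count 12 months from randomization. Section VI, Aim 6, has the intervention finished by the 6-month visit. Section V requires renewed consent for Aims 8 and 9.

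**The concern.** Three matters of unequal weight arise.

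1. **Timing (Aim 8).** A randomized comparison needs both arms measured at the same time since randomization. If one arm is seen later, anything that drifts with time, such as adherence, attendance or time in adult care, enters the difference. The label of a 12-month effect would then be wrong.
2. **Precision (Aims 3 and 8).** The estimates exist to help plan a larger trial. Leaving out an enrollment measurement of the same quantity can make them less precise than the data allow.
3. **Which contrast is the result.** The before/after wording for retention and suppression is not a randomized comparison, and nothing ties it to the between-arm difference. The two suppression cutoffs also leave a comparison of 6 with 12 months without a common definition.

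**Working it through.** **The plan's own figure.** Section VII gives about 8% as the spread of these differences. With 40 per arm and an assumed 85% suppressed or retained, the raw standard error (SE) is sqrt(2 × 0.85 × 0.15 / 40) = 0.0798, or 8.0 points. At 80% it is 8.9 and at 90% it is 6.7. The figure is therefore reproducible, but it does not reveal whether adjustment was intended: an adjusted SE of 8.0 also arises at 80% with a correlation of about 0.45.

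**Timing, Aim 8.** Let the intervention end c months after randomization, with c at most 6 (Section VI, Aim 6). The documents do not give its duration.
- Control visit: month 12.
- Earliest intervention visit: month 12 + c, with no upper limit stated.
- Retention looks back 6 months: months 6 to 12 in controls, months 6 + c to 12 + c in the intervention arm.
- c = 6: visit at month 18, look-back months 12 to 18, no overlap with controls.
- c = 3, with a prompt visit: visit at month 15, look-back months 9 to 15, 3 months of overlap.

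**Precision, scales.** Inputs: 40 per arm (Section II, Aim 3), complete data, and a baseline-to-follow-up correlation r. The documents do not give r, so a range is assumed. The SE of the analysis of covariance (ANCOVA) relative to the raw SE is sqrt((1 − r²)(2n − 3)/(2n − 4)), where n is the number per arm.

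| r | SE ratio, 40 per arm | Change | SE ratio with grouping |
|---|---|---|---|
| 0 | 1.007 | +1% | 1.006 |
| 0.3 | 0.960 | -4% | 0.966 |
| 0.5 | 0.872 | -13% | 0.891 |
| 0.7 | 0.719 | -28% | 0.764 |

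Break-even is r = sqrt(1/77) = 0.114. The last column allows for "We anticipate enrolling groups of 5 - 10 subjects" (Section VI, Aim 3) being delivery groups in the intervention arm. It assumes a group size of 7.5 and an intraclass correlation of 0.05: sqrt((2(1 − r²) × 77/76 + 6.5 × 0.05)/(2 + 6.5 × 0.05)).

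**Precision, suppression.** The model is logistic with arm and enrollment suppression, standardized to a risk difference. Assumptions: 85% suppressed at both times, no effect, 40,000 simulated trials per setting. The 32-per-arm column is 80% of 40, taken from "participation and completion thresholds >80% for each" (Section VII, Outcomes, Aim 3). SEs are in percentage points.

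| Correlation (phi) | Adjusted SE, 40 per arm (raw 8.0) | Adjusted SE, 32 per arm (raw 8.9) |
|---|---|---|
| 0 | 8.05 | 9.01 |
| 0.3 | 7.73 | 8.66 |
| 0.5 | 7.01 | 7.87 |
| 0.7 | 5.83 | 6.53 |

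At phi 0.3 and 40 per arm, the 95% half-width moves from 1.96 × 7.98 = 15.6 to 1.96 × 7.73 = 15.2 points.

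**Sparse data.** At 85%, the expected number unsuppressed at enrollment is 0.15 × 80 = 12. Fewer than 10 would occur in about 22% of trials of 80 and about 50% of trials of 64 (binomial; 10 is only an illustrative minimum). The simulation did not include a fallback to the raw difference, so it describes the adjusted estimator alone.

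**Bias, Aim 3.** In a separate simulation of 20,000 trials with randomization, common timing and no losses, the raw, change-score and adjusted differences were all centred on the true value (largest mean error 0.002 standard deviations).

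**The case against.** The strongest reply is that these are secondary estimates in a pilot, that the plan expects no significant difference, and that the gain from adjustment rests on a correlation nobody has documented. The clearest gains are on the scales, whereas the plan ties moving to a larger trial to retention and suppression. For suppression the gain at phi 0.3 is under half a point of half-width, and for retention there may be none. All of this stands, and it is why adjustment is offered as a cheap improvement and not as the correction of an error.

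It is also fair that the plan is silent on adjustment and does not exclude it, and that the optional logistic regression could include enrollment suppression. That option is exploratory, names no variables and cannot serve the scales, so it is not a commitment.

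On the before/after wording, the statistical methods already name the between-arm difference, and the Outcomes text could be read as change from baseline by arm. A reader might infer that the trial means to report an uncontrolled before/after result. The documents do not support that; a clarifying sentence is enough.

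On timing, a reader might infer that the retention windows never overlap. That holds only if the intervention ends at about month 6 or if intervention visits are late. The conflict over the time origin does not depend on it.

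**Conclusion.** The point holds at low severity, in three parts.

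1. **Wrong as written:** the Aim 8 visit has a different time origin in each arm, against the plan's own definition of 12 months from randomization. The gap is at least the time to completion, up to 6 months if visits are prompt and more if they are late. The Aim 8 difference should not be called unbiased. Renewed consent, with no stated handling of missing data, adds a further condition.
2. **Cheap improvement:** committed use of the enrollment values would change the scale SE by +1% to -28% over assumed correlations of 0 to 0.7 (40 per arm, complete data, no clustering). The effect on suppression is similar or smaller.
3. **Clarification:** the before/after comparisons and the two suppression cutoffs need a label and a common definition.

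A reader might infer that the Aim 3 estimate is biased or that the decision on a larger trial would change. Neither follows: with 1:1 randomization and complete follow-up the unadjusted Aim 3 difference is unbiased, and no change in that decision has been shown. The primary acceptability and feasibility analysis is untouched. Its stated 90% power reproduces as 0.9005, with at least 34 of 40 required and an exact one-sided alpha of 0.0238.

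**What to change.** - **Timing.** Reconcile Section IV (Aims 8/9) with the Aim 8 text in Section VII so that both arms are timed from randomization. If visits have already taken place, report time since randomization by arm and do not call the result a 12-month effect.
- **Scales.** Estimate social support, connection to clinic and self-esteem by ANCOVA on the enrollment score, with 95% confidence intervals.
- **Suppression.** Estimate a risk difference with a 95% confidence interval, adjusted for enrollment suppression at the outcome's own cutoff (400 for Aim 3, 200 for Aim 8 as now written). State in advance the minimum number unsuppressed at enrollment below which the unadjusted difference is reported.
- **Retention.** Report the unadjusted risk difference with a 95% confidence interval.
- **Aim 8.** Do not adjust for the month-6 value, which is measured after randomization.
- **Wording.** State that the between-arm difference is the result, label the before/after comparisons descriptive, and use one suppression cutoff when comparing 6 with 12 months.

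The analysis changes need SAP wording and a few lines of code, with no new data. If the correlation is zero, adjustment costs about 1% of the SE. Aligning the visit timing is a protocol wording change if visits are still to come.
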